1.2 Research content

1.2.1 Exploration of the pathogenesis of migraine in children For the subjects included in the study, blood was collected at any time during the first 2-4 hours of the headache attack in migraine patients; blood was collected at least 24 hours before and after the inter-episode period without headache attack in migraine patients. In healthy controls, blood was collected in a quiet state. Tryptophan metabolite levels were measured by ELISA. The plasma levels of tryptophan metabolites were analyzed in different groups according to the collected medical histories, and the plasma levels of migraine patients were compared with those of healthy controls by t-test: one-way ANOVA was performed between different types of migraine: correlation analysis was performed between the frequency, duration, severity and two types of migraine attacks; logistic regression was performed to screen for possible factors. The results of the above analyses were combined to explore the pathogenesis of migraine in children and to lay the foundation for the improvement of the diagnosis of migraine in children and the development of new drugs.

1.2.2 Exploration of specific diagnostic indexes for migraine in children For the subjects included in the study, blood was collected at any time during the first 2-4 hours of the headache attack in migraine patients, and blood was collected at least 24 hours before and after the headache attack in the inter-episode period in migraine patients. Tryptophan metabolite levels were measured by ELISA. The ROC curve was used to analyze the diagnostic value of the combined diagnosis of tryptophan metabolites, and tryptophan metabolites, and the area under the curve (AUC) of tryptophan metabolites and the combined diagnostic indexes of both were subjected to independent sample t-test to analyze whether there was a statistical difference between the three, and the diagnostic test evaluation indexes were used to evaluate the combined diagnosis of tryptophan metabolites, and tryptophan metabolites respectively, and to evaluate them as The possibility and accuracy of the

specific diagnostic index of migraine in children were evaluated.

2. The proposed research method, technical route, experimental protocol and feasibility analysis.

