2.1 Experimental protocol

2.1.1 Inclusion and exclusion criteria of study subjects

Case group inclusion criteria:(1) Age 4-18 years old, male and female are not limited. (2) Meet the diagnostic criteria of ICHD-3 with aura, without aura, and chronic migraine. (3) Migraine was diagnosed by two or more specialized neurologists. (4) PedMIDAS score > 11 (5) Migraine had never been treated (6) Patients and families gave informed consent to the study purpose, significance, risks, benefits, and informed consent. Source: Department of Pediatrics Outpatient and Inpatient Unit, Oilu Hospital. Shandong University

Inclusion criteria for the control group:(1) Age 6-18 years, male and female. (2) Did not meet the diagnostic criteria of ICHD-3 migraine and other headaches. (3) Physical health allowed their participation in the study. (4) Patients and their families gave informed consent to the study purpose, significance, risks, benefits, and information of the study. Source: Department of Pediatrics Outpatient and Inpatient Unit, Oilu Hospital. Shandong University.

Exclusion criteria:

(1) presence of drug overdose (2) autoimmune diseases (3) neurological diseases other than migraine, intracranial masses (4) congenital or hereditary diseases (5) diabetes, bronchial asthma, cardiovascular diseases, pulmonary diseases (6) other types of primary and secondary headache.

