2.1.2 Data collection

(1) Data sources: questionnaires, outpatient medical records and auxiliary examination results.

(2) Collection methods: questionnaire survey, medical records review, blood collection.

(3) Data composition: Basic personal information, migraine triggering factors, clinical features of headache, medication, past medical history, ancillary examinations, and blood samples were collected from all enrolled headache patients.

① Basic personal information included name, gender, age, height, weight (calculated BMI) cultural level, residence address, and contact information.

② Migraine triggering factors: genetic factors, endocrine (menstruation), diet (cheese, chocolate, puffed food), psychological factors (sleep, anxiety, depression, emotional stress, etc).

③ Clinical characteristics of headache included: whether the patient was in the attack phase or inter-attack phase, the location of the patient's headache, the nature of the headache, the degree of pain (assessed using the visual analog scale VAS Appendix), the duration of the disease (years), the frequency of the headache, the duration of each headache, the time of the last pain, the presence of aura, aura symptoms, concomitant symptoms (photophobia, phonophobia, nausea, vomiting, gastrointestinal

symptoms),exacerbation and remission. The information of each headache, duration of last pain,presence of aura, aura symptoms, concomitant symptoms (photophobia, photophobia.nausca, vomiting, gastrointestinal symptoms), aggravation and relief factors, familyhistory, etc.

④Also record medication use, past medical history, ancillary test results such asroutine blood, liver function, kidney function, lipids, blood glucose, ECG, TCD, headCT,head MRIhead MRA examination,etc.PedMIDAS scale score, migraine treatment efficacy assessment scale, headachediary

⑤5ml of venous blood

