2.1.3 Study method

(1) The trial was reviewed by the Research Ethics Committee of Qilu Hospital of Shandong University. Patients were obtained from the pediatricoutpatient clinic of Qilu Hospital of Shandong University, with written permissionfrom parents or guardians and, where appropriate, consent from the children. Theinvestigators were responsible for design, data collection, analysis, and interpretation. Data were collected by field researchers. and all data were confidential for theduration of the trial; trialists and data analysts could not communicate data with eachother. Eligible healthy children and children with migraine were recruited in the first step and basic information about the children and headache characteristics were obtainedby the site staff, and blood was retained from the study subjects for Elisa assay, respectively.

(2) Method for determination of tryptophan metabolite content:

①Timing of blood collection

In the case group, blood was collected at any time during the first 2-4 hours of themigraine attack; in the inter-migraine attack group, blood was collected at least 24hours before and after the headache-free period. In the healthy control group, bloodwas collected in a quiet state.

②Storage and testing methods

5 ml of elbow venous blood was collected from patients and healthy children inpurple tubes, and the samples were immediately transferred to ice-cold glass tubescontaining a mixture of anticoagulant and protease inhibitor, and centrifuged at 3000rpm for 5 minutes at 4°C. The supernatant was stored at -80°C, and tryptophanmetabolite levels were measured by ELISA, and the case and control groups were compared and analyzed.

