2.1.4 Data analysis

Statistical analysis was performed using SPSS26.0 software analysis, and statisticaldata were tested for normality, and the mean standard deviation ($x + S$) was used formeasurement data that conformed to the normal distribution, and one-way ANOVAwas applied for comparison between the three groups, and t-test for two independentsamples was used for comparison between two groups. The correlation between theplasma levels between migraine attacks and the duration of the disease was analyzedby SPSS26.0 correlation analysis.

(1) After completing the questionnaire survey, the researchers collected data

and analyzed the risk of migraine in children due to the interaction of multiple factors, and used logistic regression to screen the indicators related to the risk of migraine in children due to the interaction of multiple factors, and established an early assessment model of migraine in children to achieve early detection, early diagnosis and early prevention of migraine in children.

(2) Based on the collected medical history, different group analyses were performed, and the plasma levels of tryptophan metabolites in migraine patients were compared with those in healthy controls by t-test; one-way ANOVA was performed on the plasma levels of tryptophan metabolites between different types of migraine; correlation analyses were performed between the frequency, duration, severity and two types of migraine attacks; and logistic regression was performed to screen for possible influences on the risk of migraine in children. Logistic regression was performed to screen the factors that may influence the diagnosis of migraine in children.

(3) To analyze the diagnostic value of tryptophan metabolite and tryptophan metabolite combined diagnosis by ROC curve, and to analyze whether there is any statistical difference between the three diagnostic indexes by independent sample t-test, and to evaluate the diagnostic indexes of tryptophan metabolite and tryptophan metabolite combined diagnosis by diagnostic test, and to evaluate the diagnostic indexes of tryptophan metabolite and tryptophan metabolite combined diagnosis as the possibility and accuracy of specific diagnostic indexes for migraine in children were evaluated.

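### The comparison of migraine types is a one-way ANOVA that leaves out attack phase, although phase is recorded and decides when blood is drawn

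*SAP*

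**What the plan says.** The comparison appears twice in the SAP. Section 1.2.1 says "one-way ANOVA was performed between different types of migraine", and 2.1.4 item (2) says "one-way ANOVA was performed on the plasma levels of tryptophan metabolites between different types of migraine". Neither place names a second factor, a stratum or a restriction to one phase. The enrolled types are given in 2.1.1: "Meet the diagnostic criteria of ICHD-3 with aura, without aura, and chronic migraine".

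Phase enters the plan elsewhere. Section 2.1.2 records "whether the patient was in the attack phase or inter-attack phase". Section 2.1.3 gives separate collection rules: "In the case group, blood was collected at any time during the first 2-4 hours" of the attack, and "in the inter-migraine attack group, blood was collected at least 24hours before and after the headache-free period". Section 1.2.1 describes both collections under the single label of migraine patients.

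**The concern.** The plan separates the two phases when blood is drawn and records which one applies, so it treats phase as something that may affect the measurement. It then compares types without it. If one type is sampled mostly in attacks and another mostly between attacks, the type means carry part of the phase effect.

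Such an imbalance is foreseeable. Chronic migraine is one of the enrolled types, and an inter-attack sample depends on headache-free time, which may be harder to find in those children. The error can go either way: a difference between types that is only a difference in timing, or a true type difference cancelled by timing.

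**Working it through.** The SAP states no sample size, power or alpha, so there is no figure of its own to reproduce. Everything below is an illustration under assumed inputs.

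**Assumptions.** One sample per child; SD 1 within phase; attack samples shifted by δ; three types with n children each and attack shares p₁, p₂, p₃; F-test at 5%.

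**Formula.** With no type effect, the one-way F-test has approximate noncentrality λ = n δ² Σ(pᵢ − p̄)² / σ², where σ² = 1 + δ² × mean of pᵢ(1 − pᵢ).

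**Equal shares.** Σ(pᵢ − p̄)² = 0, so λ = 0 and false rejection is 5%. If the phase counts are exactly balanced by design it is lower (2.5 to 4.5% for shifts of 0.5 to 1.0 SD and 20 or 40 per type), because phase variance stays in the error term.

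**Shares 40/40/80%.** p̄ = 0.533, Σ(pᵢ − p̄)² = 2 × 0.133² + 0.267² = 0.1067, and the mean of pᵢ(1 − pᵢ) = (0.24 + 0.24 + 0.16)/3 = 0.213.

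| n per type | δ (SD) | n δ² × 0.1067 | σ² | λ | False rejection, type only | With phase in the model |
|---|---|---|---|---|---|---|
| 30 | 0.5 | 0.80 | 1.053 | 0.76 | 11% | about 5% |
| 30 | 0.8 | 2.05 | 1.137 | 1.80 | 20% | about 5% |
| 50 | 0.5 | 1.33 | 1.053 | 1.27 | 15% | about 5% |
| 50 | 0.8 | 3.41 | 1.137 | 3.00 | 32% | about 5% |

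Simulation agrees with these values to within about two points.

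**Milder cases.** For shifts of 0.5 to 0.8 SD, false rejection is about 6% at shares 40/40/50% and 6 to 11% at 40/40/60%. For shifts of 0.2 to 0.3 SD it stays at 5 to 9% at every share examined, up to 40/40/80%.

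**Masking.** Take a true effect of 0.6 SD in the third type and shares 80/80/40%. The observed gap shrinks to 0.6 − 0.4δ, which is 0.40 SD at δ = 0.5 and 0.28 SD at δ = 0.8. Simulated power without phase is 16 to 32% (30 per type) or 26 to 51% (50 per type). With phase it is about 57% or 81%.

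**One sample or two.** Section 2.1.3 speaks of separate groups and 2.1.2 lists a single 5 ml draw, which favours one sample. Section 1.2.1 describes both collections in migraine patients, which fits one or two. If every child gave both samples, phase would be balanced across types and the confounding above would vanish, but the two samples from a child would be correlated. With 30 or 50 per type, a shift of 0.5 SD and no type effect, treating all samples as independent gives:

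| Within-child correlation | Type only | Type plus phase as an ordinary factor | Types within one phase |
|---|---|---|---|
| 0.3 | 9% | 10% | 5% |
| 0.5 | 12% | 13% | 5% |
| 0.7 | 15 to 16% | 17% | 5% |

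So adding phase as an ordinary factor is sound only with one sample per child.

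**The case against.** The strongest reply is that the harm is conditional three times over: one sample per child, a real phase effect, and a phase mix that differs by type. The SAP shows none of these, and its aims are exploratory. At mild imbalance or small shifts the inflation is slight. This stands as a limit on size. It does not justify leaving a recorded and foreseeable source of variation out of the comparison when including it is cheap.

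Three stronger readings are tempting, and the document does not support them.

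- *The case-control t-test is undefined.* 'Case group' does have two senses: "Case group inclusion criteria" in 2.1.1 covers every eligible migraine child, while 2.1.3 uses the term for attack samples beside an inter-attack group. But 1.2.1 and 2.1.4 word the t-test in terms of migraine patients, the label that 1.2.1 uses for both phases. This is loose terminology to tidy, not a defect that carries the point.
- *The ANOVA "applied for comparison between the three groups" must be attack, inter-attack and control.* It could equally be the three migraine types of 2.1.1. Either way, the type comparison still omits phase.
- *The correlations also ignore phase.* The two types of attack named there are undefined and may be the two phases, so this cannot be claimed.

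**Conclusion.** The point holds for the type comparison. As written, it has type as its only factor and does not say which phase's samples enter or how phase is handled. With one sample per child, a phase effect and unequal phase shares, it can reject falsely or miss a true difference. At attack shares of 40/40/80%, a 0.5 to 0.8 SD shift and 30 to 50 per type, false rejection is 11 to 32% against a nominal 5%.

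Every input to that range is assumed. A reader might infer that the types are in fact sampled in different phases; nothing in the SAP shows that, and at equal shares there is no inflation. The omission is plain in the text, but the size of any bias is unknown. It should be corrected before analysis.

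**What to change.** 1. State whether each child gives one blood sample or two.
2. Then do one of the following: compare types within phase (valid in either case); with one sample per child, add the recorded phase as a factor; or with two samples per child, use a model with phase and a within-child term.
3. As secondary tidying, use 'case group' in one sense in 2.1.1 and 2.1.3, say which phase's samples enter the t-test against controls, and name the three groups and the two types of attack in 2.1.4. The authors should supply the grouping they intended.

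**Cost.** No new data, since phase is already recorded. With one sample per child, adding phase uses one degree of freedom (error degrees of freedom 86 instead of 87 at 30 per type). At equal shares with no phase effect, power for a 0.6 SD type effect changes by at most 0.5 point. At shares 40/40/80% with no phase effect, it falls from about 65% to 57% (30 per type) or from 88% to 81% (50 per type). If a type is never sampled in one phase, the comparison holds only within the other phase, or by assuming one common phase shift; the report would have to say so.

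### The ROC analysis can show only that the metabolites separate migraine from no headache disorder, not that they are specific to migraine, and the blood-draw phase entering it is not fixed

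*SAP*

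**What the plan says.** **Purpose.** Section 2.1.4(3) introduces the analysis as "To analyze the diagnostic value of tryptophan metabolite and tryptophan metabolite combined diagnosis by ROC curve" and ends by saying that "the possibility and accuracy of specific diagnostic indexes for migraine in children were evaluated". Section 1.2.2 has the same aim; there the possibility and accuracy of the "specific diagnostic index of migraine in children were evaluated".

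**Who is sampled.** Section 2.1.1 admits cases with ICHD-3 migraine that has never been treated and with "4) PedMIDAS score > 11". Controls are children who "Did not meet the diagnostic criteria of ICHD-3 migraine and other headaches". The exclusion list includes "6) other types of primary and secondary headache". Section 2.1.3(1) describes recruitment of two kinds of children only: healthy children and children with migraine.

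**When blood is drawn.** Migraine patients are sampled in two phases. One is early in an attack. For the other, section 1.2.2 says that "blood was collected at least 24 hours before and after the headache attack in the inter-episode period in migraine patients". Section 1.2.1 adds: "In healthy controls, blood was collected in a quiet state". Section 2.1.3(2) repeats the timing for all three groups. The ROC description in 1.2.2 mentions only the two migraine draws, and 2.1.4(3) mentions neither groups nor phases.

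**The concern.** A specific diagnostic index is naturally taken to mean one that marks migraine out from the conditions it could be confused with, which are chiefly other headaches. Those children are excluded from the study. A reader of the eventual report could take a good AUC as evidence that the marker identifies migraine among children who present with headache, when the data speak only to migraine versus no headache disorder.

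The second issue is that two phases of migraine blood are collected and the plan does not say which enters the ROC. That leaves a choice open until after the data are seen. If the phases are pooled, the reported AUC depends partly on how many samples of each kind happened to be collected.

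**Working it through.** The SAP states no sample size, target AUC, cut-off, sensitivity or specificity, so there is no figure of its own to reproduce. The first step below is a comparison of the text. The others are illustrations on assumed inputs.

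**1. What the sample can estimate**

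| Quantity | Children needed | In the planned sample? |
|---|---|---|
| Sensitivity in never-treated migraine, PedMIDAS above 11 | Such cases | Yes (2.1.1) |
| Specificity in children with no headache disorder | Healthy controls | Yes (2.1.1, 2.1.3) |
| Specificity in children with another headache | Children with non-migraine headache | No: excluded in 2.1.1, not recruited in 2.1.3 |

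The third quantity has zero contributing children at any sample size. Enlarging the study would not change this.

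**2. What pooling the phases would do**

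For one fixed score, the empirical AUC is an average over all case-control pairs. Splitting the pairs by the phase of the case sample gives

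pooled AUC = w × AUC(attack) + (1 − w) × AUC(inter-attack),

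where w is the attack share of case samples. With assumed phase AUCs of 0.85 and 0.60:

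- w = 0.25: 0.25 × 0.85 + 0.75 × 0.60 = 0.6625
- w = 0.50: 0.50 × 0.85 + 0.50 × 0.60 = 0.7250
- w = 0.75: 0.75 × 0.85 + 0.25 × 0.60 = 0.7875

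With 0.85 and 0.70 the same shares give 0.7375, 0.7750 and 0.8125. With equal phase AUCs, pooling changes nothing. The identity does not carry over to a combined index that is refitted in each phase, so it illustrates the single-marker ROC and not every index in the plan.

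**3. What separating the phases costs in precision**

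The Hanley-McNeil variance, with A the AUC, n1 cases, n0 controls, Qa = A/(2 − A) and Qb = 2A²/(1 + A), is

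Var = [A(1 − A) + (n1 − 1)(Qa − A²) + (n0 − 1)(Qb − A²)] / (n1 × n0).

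At an assumed A = 0.75: A(1 − A) = 0.1875, Qa − A² = 0.6000 − 0.5625 = 0.0375, and Qb − A² = 0.6429 − 0.5625 = 0.0804.

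- 60 v 60: (0.1875 + 59 × 0.0375 + 59 × 0.0804)/3600 = 0.00198; SE 0.0445; half-width 1.96 × SE = 0.087
- 30 v 60: (0.1875 + 29 × 0.0375 + 59 × 0.0804)/1800 = 0.00334; SE 0.0578; half-width 0.113

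The same formula gives 0.107 to 0.139 going from 40 v 40 to 20 v 40, and 0.067 to 0.088 going from 100 v 100 to 50 v 100. The halving of cases assumes that each child is sampled in one phase only and that the phases are equally represented. If every case gave both samples, 60 cases would remain in each phase and the 60 v 60 half-width would apply to each.

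**The case against.** The strongest reply is that the plan is exploratory and claims little. Section 1.2.2 is headed as an exploration, and the text speaks of possibility and accuracy. A reader might infer that the SAP declares a specific index established; it does not, and that part of the reply stands. What remains is that the word specific sets the question the AUC will be used to answer, and an exploratory label does not supply the missing comparison group.

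Three other stronger readings are tempting and are not supported:

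- *The comparison group is undefined.* Section 1.2.2 omits the control draw, so one might infer that the ROC could be attack versus inter-attack. But healthy controls are the only non-migraine group in the plan, and 2.1.3 and 2.1.4(2) compare patients with them. The class is effectively fixed, though it should be named.
- *Sampling times are missing.* They are given in 1.2.1, 1.2.2 and 2.1.3. Only their use in the ROC is open.
- *The phases will be pooled.* No text says so. Section 2.1.3 lists attack, inter-attack and control groups, and 2.1.4 plans an ANOVA of three groups, which leans towards keeping them apart. Section 2.1.4(2), however, compares migraine patients as a whole with controls. The text is ambiguous, so the pooling effect is conditional.

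It is also fair to say that the PedMIDAS and never-treated limits are declared eligibility choices. They define the population to which the result applies and are not errors.

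**Conclusion.** The point holds in a limited form. The ROC can estimate discrimination of never-treated migraine with PedMIDAS above 11 from children without a headache disorder, which is a legitimate exploratory result. It gives no information on specificity to migraine among children with headache. That follows from the eligibility rules alone and needs no assumption beyond reading specific in its ordinary diagnostic sense, a term the SAP does not define.

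The open phase is a gap in specification. Its effect on the AUC cannot be sized from the document. Under the assumed phase AUCs of 0.85 and 0.60, the pooled value ranges over 0.7875 − 0.6625 = 0.125 as the attack share goes from 25% to 75%; it would be nil if the phases discriminate equally. All AUCs, shares and sample sizes used here are assumptions.

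A reader might infer that the study is invalid or that the eligibility criteria must change. Neither follows: what needs correcting is the stated contrast, the phase and the reach of the conclusion. Nor does the point extend to the logistic model in 2.1.4(1), which is a separate matter.

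**What to change.** In sections 1.2.2 and 2.1.4(3):

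- name the ROC contrast as migraine cases versus healthy controls;
- report AUC, sensitivity and specificity with 95% CIs separately for attack and inter-attack samples, each against the controls;
- limit the conclusion to migraine, as enrolled, versus no headache disorder, and state that specificity against other headaches is not estimated.

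The change is one of wording plus phase-specific ROC analyses. It needs no new patients or assays, because section 2.1.2 already records whether the patient was in the attack or inter-attack phase. The costs are a narrower claim, more results to report (two phases for each of the three indexes the plan mentions makes six AUCs) and, if each child is sampled in one phase only, the wider CIs shown above. A claim of specificity against other headaches would need a comparison group with those headaches, which is beyond this change.
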